13 STATISTICAL CONSIDERATIONS

13.1 Statistical hypothesis

We will use a mixed-effects regression model that accounts for clustering (patients nested within providers) to compare the average number of days from surgery to the initiation of radiation between treatment and control groups. We hypothesize that utilization of study therapy will significantly reduce the average number of days to initiation of adjuvant radiation.

13.2 Sample size determination

The sample size calculation was based on the current average number of days to adjuvant radiation in our patients with advanced-stage head and neck cancer, 72.8 days (Standard Deviation 16.2 days) based on the most recent 100 patients that fit criteria. Our goal is to reduce the current average number of days to adjuvant radiation down to 57.2 days since this has been shown to improve survival.

Assuming Group A mean =72, Group B mean = 57.2, and the common SD =16.2, a two sample t-test with 20 patients in each group will provide 80% power with an alpha = 0.05. Note that the estimated SD = 16.2 days includes variation by provider as well as random variation and thus the estimated power is likely to be conservative as control of provider variation using a mixed-effects model should provide additional power.

13.2.1 Statistical justification for change in hypothesis

The sample size calculation was modified due to an interim review with the clinical trials team, the investigators, and the safety and monitoring committee. It was determined by expert opinion and previously established data, that a reduced group B mean was clinically reasonable based on similar studies and prior results seen in similar situations, and this results in a reduced sample size necessary to achieve 80% power.

13.3 Population for analyses

13.3.1 Evaluable for toxicity

Subjects who have taken one dose of study therapy will be evaluable for toxicity.

13.3.2 Evaluable for the primary endpoint

Subjects who have completed study therapy lead-in, undergone surgery, and received one treatment of adjuvant radiation will be evaluable for the primary endpoint. Patients who do not start adjuvant radiation will be replaced.

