2 BACKGROUND

2.1 Hypothesis

Using celecoxib comprehensively throughout treatment starting 1 to 7 days prior to surgery to the end of adjuvant radiation, will improve pain control, reduce opioid use, and improve QOL and functional status, leading to improved compliance with adjuvant radiation which is known to correlate with improved survival outcomes.

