2.3 The Effect of Pain Control on Overall Survival and Study Objective Rational

Currently, pain control throughout therapy is a major issue for patients with advanced-stage head and neck cancers (sinonasal, oral cavity, oropharynx, larynx, and hypopharynx) undergoing primary surgical resection and then adjuvant therapy. In order to maximize survival outcomes, patients treated with surgery and then adjuvant therapy (ie: radiation or chemoradiation) need to start adjuvant therapy within 8 weeks or approximately 60 days after surgery and need to minimize delays or gaps in adjuvant treatments. A recent NCDB study in this patient population demonstrated 5-year OS differences of 67% versus 52% in these 2 cohorts (initiation of adjuvant therapy <50 days versus >50 days).¹ This has been confirmed in a systematic review and other evaluations of large aggregated national datasets.²⁻⁵ Based on our experience and retrospective examination, we have identified that the leading culprit in these cases is pain management and functional issues. These issues contribute to increased narcotic utilization and reduced recovery after surgery with weight loss, poor oral intake, and reduced overall strength, resulting in delays in initiating adjuvant therapy. This post-surgical condition of the patient is also a significant contributor to missed treatments once adjuvant therapy has begun. Based on retrospective examination, it is estimated a significant percentage of patients do not achieve the recommended rate of compliance.

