4.2 Randomization and Blinding

Patients who meet all criteria for enrollment will be randomly assigned to receive celecoxib (Arm 1) or placebo (Arm 2). Patients will be randomized through the OnCore system in a 1:1 ratio between Arm 1 and Arm 2 and stratified by treating provider.

To preserve the blind, only the Investigational Drug Services Pharmacy personnel at Huntsman Cancer Institute will know treatment assignments. Access to unblinded data/documents will be controlled by the pharmacy to ensure the blind is maintained. Every effort will be made to blind both the patient and the investigator to the treatment assignment, but the inadvertent unblinding of a patient may occur. If an investigator, site personnel, or patient is inadvertently unblinded, the unblinding will not be sufficient cause for the patient to be discontinued from study treatment or excluded from study analyses.

In the case of an emergency, the investigator has the sole responsibility for determining if the unblinding of a patient's treatment assignment is warranted. Patient safety must always be the first consideration in making such a determination. If the treating investigator decides that unblinding is warranted, the investigator should contact the investigational pharmacy for treatment assignment.

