4.3 Number of Patients

A total of 40 evaluable patients will be enrolled in this study with 20 patients randomized to each arm: 20 patients will receive celecoxib and 20 patients will receive placebo. It is expected that 25% of patients who start study therapy and undergo surgery will not start adjuvant radiation. Patients who do not start adjuvant radiation will be replaced. Taking this into account, it is estimated that 53 patients will be randomized to result in 40 evaluable patients.

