5.1 Inclusion Criteria

Yes/No (Response of "no" = patient ineligible)

5.1.1 _____ Male or female subject aged ≥ 18 years.

5.1.2 _____ Advanced-stage (overall stage III and IV) head and neck cancers (sinonasal oral cavity, oropharynx, larynx, and hypopharynx) undergoing surgical resection and then adjuvant radiation. Primary and recurrence cases are acceptable.

5.1.3 _____ Karnofsky Performance Status of ≥ 70 .

5.1.4 _____ Adequate organ function demonstrated on labs drawn during the screening window and defined as:

- Hematologic:
 - Hemoglobin ≥ 10 g/dL
- Hepatic:
 - Total Bilirubin ≤ 2 mg/dL
 - AST(SGOT)/ALT(SGPT) $\leq 2.5 \times$ institutional ULN
 - Albumin > 3.5 g/dL
- Renal:
 - eGFR ≥ 30 mL/min/1.73m² or creatinine clearance ≥ 30 mL/min by Cockcroft-Gault:
 - Males:
$$\frac{(140 - \text{age}) \times \text{weight}[kg]}{\text{serum creatinine } \left[\frac{mg}{dL} \right] \times 72}$$
 - Females:
$$\left(\frac{(140 - \text{age}) \times \text{weight}[kg]}{\text{serum creatinine } \left[\frac{mg}{dL} \right] \times 72} \right) \times 0.85$$
 - Serum potassium within normal limits.

- 5.1.5** _____ Negative serum or urine pregnancy test at screening for women of childbearing potential.
- 5.1.6** _____ Highly effective contraception for female subjects throughout the study and for at least 5 days after the last dose of study therapy if the risk of conception exists (see [section 8.6](#)).
- 5.1.7** _____ Recovery to baseline or \leq Grade 1 CTCAE v5.0 from toxicities related to any prior treatments, unless AE(s) are clinically nonsignificant and/or stable on supportive therapy.
- 5.1.8** _____ Willing to maintain a diary of all opioids used during the trial for the treatment of pain.
- 5.1.9** _____ Able to provide informed consent and willing to sign an approved consent form that conforms to federal and institutional guidelines.
- 5.1.10** _____ Subject has verbally confirmed they are willing to complete adjuvant radiation therapy if recommended after surgery per protocol.
- 5.1.11** _____ Adjuvant radiation has been recommended by the institutional treatment planning conference with the best available data, but will be confirmed based on final surgical pathology.

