6 STRATIFICATION FACTORS

At the time of randomization, patients will be stratified by the treating provider.

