7 TREATMENT PLAN

7.1 Administration Schedule

Celecoxib 200 mg/20 mL or placebo will be taken orally or by feeding tube twice daily (every 12 hours \pm 2 hours) without regard to food. Patients will complete 1 to 7 day(s) of study therapy prior to surgery and continue regular dosing until the completion of radiation therapy.

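### The primary analysis keeps only patients who completed the lead-in, had surgery and started radiation; no planned analysis of that endpoint keeps the expected 25% who do not start

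*Combined protocol and SAP*

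**What the plan says.** Section 13.3.2 states who enters the main analysis: "Subjects who have completed study therapy lead-in, undergone surgery, and received one treatment of adjuvant radiation will be evaluable for the primary endpoint". It adds that patients who do not start radiation are replaced. Section 4.3 repeats the replacement rule and gives the expected loss: "It is expected that 25% of patients who start study therapy and undergo surgery will not start adjuvant radiation". It plans about 53 randomised to obtain 40 evaluable, 20 per arm.

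Section 13.4.1 gives one Gaussian mixed model of days from surgery to radiation, which a patient without a start date cannot enter. No all-randomised set, sensitivity analysis or other handling of non-starters is described for this endpoint. Section 13.4 promises descriptive statistics by arm for every study variable, but neither non-start nor its reason is named as one.

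The protocol expects celecoxib to act on recovery, "leading to improved compliance with adjuvant radiation" (section 2.1). Section 2.3 blames pain and poor recovery after surgery, "resulting in delays in initiating adjuvant therapy". In the other direction, section 3.1.4 and Table 3 in section 8.4 list serious gastrointestinal and cardiovascular harms.

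Some non-starts will have another cause. Under section 5.1.11 the need for radiation "will be confirmed based on final surgical pathology", and section 7.3.4 lists no need for radiation among the reasons to stop study treatment. The 25% is not split by reason.

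**The concern.** Completing the lead-in, having surgery and starting radiation are all determined after randomisation. If the drug changes how many patients start, or which ones, the starters in the two arms are no longer comparable groups. Mean days can then differ because the mix of starters differs, not because anyone started sooner. Replacing non-starters restores the count of 40 but not the comparison.

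The excluding event lies close to the outcome under test: the process thought to delay radiation can also prevent it. Without start rates and reasons by arm, and one analysis that keeps the non-starters, a reader of the primary result cannot tell faster starts from a different mix of starters.

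A smaller point is the lead-in condition, which can remove a patient who does have a valid start date. Such patients may be few; the documents give no number. The condition is also hard to apply, because the lead-in is described in different ways: "Patients will complete 1 to 7 day(s) of study therapy prior to surgery" in section 7.1, three to seven days in section 7.3.3, and in section 10.2 both a start six days before surgery and a range of 1 to 7 days.

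**Working it through.** **Inputs from the protocol.** Means 72 and 57.2 days (difference 14.8), SD 16.2, 20 per arm, alpha 0.05 (section 13.2); two-sided test (section 13.4.1); 25% non-start and 53 randomised (section 4.3).

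**Step 1: the plan's own figures.**
- Standard error = 16.2 × √(2/20) = 5.12. Noncentrality = 14.8 / 5.12 = 2.89. Two-sided t-test power with 38 degrees of freedom = 0.804. The stated 80% reproduces.
- 40 / 0.75 = 53.3, against the stated 53.
- 53 × 0.25 = 13.25, so about 13 patients fall outside the primary analysis.

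**Step 2: a model for the shift (assumed, not in the documents).** Each patient has a latent time to radiation, normal with SD 16.2. A patient does not start when a second latent variable exceeds its upper-f cut-off, where f is the arm's non-start rate. The two variables have correlation ρ. Then:

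- starters' mean = latent mean − ρ × 16.2 × λ(f), where λ(f) = φ(z) / (1 − f) and z is the (1 − f) normal quantile;
- λ(0.15) = 0.274, λ(0.20) = 0.350, λ(0.25) = 0.424, λ(0.30) = 0.497, λ(0.35) = 0.570;
- shift against celecoxib = ρ × 16.2 × [λ(placebo) − λ(celecoxib)], for the same ρ in both arms.

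**Step 3: shift and power.** Section 13.2 derives the SD of 16.2 from past patients' days to adjuvant radiation, so it describes patients with a start date. Power is therefore computed with the starters' SD held at 16.2, as the noncentral t probability at (14.8 − shift) / 5.12.

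| Non-start, placebo / celecoxib | ρ | Shift against celecoxib (days) | Difference shown | Noncentrality | Power |
|---|---|---|---|---|---|
| any rates | 0 | 0 | 14.8 | 2.89 | 0.80 |
| 30% / 20% | 0.3 | 0.71 | 14.09 | 2.75 | 0.76 |
| 30% / 20% | 1.0 | 2.38 | 12.42 | 2.42 | 0.66 |
| 35% / 15% | 0.3 | 1.44 | 13.36 | 2.61 | 0.72 |
| 35% / 15% | 1.0 | 4.79 | 10.01 | 1.95 | 0.48 |

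If 16.2 is instead taken as the latent SD throughout, truncation shrinks the starters' SD and power appears to rise, to 0.90 at 30% / 20% with ρ = 1. That is an artefact of where the SD is placed. Conversely, a starters' SD of 16.2 implies a somewhat larger latent SD, so the shifts in the table are slightly understated.

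**Step 4: the reverse direction.** At 15% / 35% and ρ = 0.5, the shift is 0.5 × 16.2 × (0.570 − 0.274) = 2.4 days in favour of celecoxib. With no true effect, the two-sided test rejects in about 7.7% of trials (7.4% with the starters' SD held at 16.2).

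**Step 5: equal rates.** At 25% in both arms with the same ρ, the shift is zero. With ρ = 0.7 on placebo and 0.3 on celecoxib it is 0.4 × 0.424 × 16.2 = 2.7 days against celecoxib. Equal start rates alone are therefore not a full reassurance.

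**Step 6: what a worst-rank check can do.** Non-starters are ranked last in a Wilcoxon test (simulated, unstratified, true difference 14.8 days, equal rates).
- 27 and 26 patients with 25% non-start: power about 40-45%.
- If half of the non-starts have no indication (assumed) and are removed, about 53 × 0.875 = 46 patients remain, with 0.125 / 0.875 = 14% non-start. At 23 per arm, power is about 55-60%.
- No effect on time, 15% / 35% non-start and ρ = 0.5: it rejects about 15% of the time, purely because start rates differ.

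**The case against.** The endpoint has no value in a patient who never receives radiation, so an analysis of starters is natural, and this is a single-site pilot. That stands as a reason to keep the mean-days model. It does not remove the need to label the estimate and report the losses, because the plan has a powered hypothesis and a two-sided p-value.

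Non-start may be mostly pathology-driven and unrelated to arm. Some will be, and the larger that share, the smaller any shift. The documents do not give the share.

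Blinding is in place: "Every effort will be made to blind both the patient and the investigator to the treatment assignment". It guards against knowledge of the arm, but cannot prevent a drug effect on recovery.

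Reporting is partly covered. Start dates are collected retrospectively (section 12.1), a discontinuation reason exists (section 7.3.4) and descriptive statistics are by arm (section 13.4). The gap is therefore narrow: non-start and its reason are not named, and patients who leave the study (section 7.3.5) may have neither on record.

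The worst-rank test has low power and mixes timing with start rate. That is true, so it can serve only as a consistency check.

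A reader might infer that the plan is biased towards celecoxib. The documents do not support that: under the protocol's own mechanism the modelled shift goes against the drug. Nor can that direction be assumed, because the listed harms offer an opposite route. A reader might also infer that non-starters vanish from the whole trial. They remain in the toxicity set (section 13.3.1), and the secondary models (section 13.4.2) state no population.

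**Conclusion.** The concern holds for the primary endpoint and should be fixed. Its only planned analysis depends on events after randomisation that the drug could plausibly influence, and about 13 of 53 patients are expected to be left out. The difference in mean days may be shifted either way; size and direction cannot be derived from the documents.

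The figures above are illustrations. They rest on a normal latent time, a true difference of 14.8 days, an SD of 16.2, and chosen rates and correlations. The upper ends need a correlation of 1.0. With zero correlation, or with equal rates and equal correlation, the shift is zero, and differences in the share and kind of starters could also offset each other. The sample-size arithmetic is not at fault, and the finding does not show that the starters-only result would be wrong, only that it could not be judged as the plan stands.

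**What to change.** 1. Keep the mean-days model as primary and label it conditional on surgery and on starting radiation. Surgery stays a condition because it is day 0. Delete the lead-in condition, so that every operated patient with a radiation start date is analysed as randomised. State that this slightly changes the primary population, and that these patients count towards the 40 evaluable and are not replaced. Separately, reconcile the lead-in descriptions in sections 7.1, 7.3.3 and 10.2.
2. Report by arm the numbers randomised, operated on, started, not started, and lost or withdrawn, with the reason for each non-start. Classify absence of a radiation indication on final pathology blind to arm.
3. Before unblinding, pre-specify one sensitivity analysis that keeps the remaining non-starters. One example is a worst-rank test stratified by provider, matching the design: "At the time of randomization, patients will be stratified by the treating provider". Describe it as a low-power consistency check that also reacts to a difference in start rates alone.

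Cost: a protocol amendment with IRB review (section 16.6), some chart abstraction, one extra analysis and a small change in the primary population. No extra patients.

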13.4 Statistical Analyses

Appropriate descriptive statistics will be reported for all study variables, stratified by treatment arm. These will include mean, standard deviation and 95% confidence interval for continuous study variables. For categorical study variables the descriptive statistics will include counts, proportions and 95% binomial confidence intervals.

13.4.1 Primary endpoint

The primary endpoint is the number of days from surgery to adjuvant chemotherapy. A Gaussian mixed effects regression model will be used to compare the average number of days from surgery to the initiation of radiation between treatment and control groups. The model will contain fixed effects for treatment arm and provider and a nested random effect for patient within provider. The mean difference between treatment groups, two-sided p-value and 95% confidence interval will be calculated from the model.

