⁷ Appendix 8: Treating Investigator Patient Assessment Guidance to be filled out by the treating investigator at the time of physical exam.

⁸ See Appendix 8: Treating Investigator Patient Assessment Guidance

⁹ Hematology to include CBC with platelets and differential.

¹⁰ Chemistry to include a complete metabolic panel (CMP).

¹¹ All women of child-bearing potential must have a negative pregnancy test 7 days prior to surgery.

¹² Only required if there is a known history of HIV, hepatitis B, or hepatitis C to confirm eligibility.

¹³ The radiation oncology consultation should be completed prior to registration if possible. This will include a discussion of the indications for adjuvant radiation treatment, a typical treatment course, and the anticipated/possible side effects so the subjects know what to expect if enrolled on trial.

¹⁴ Prior to surgery, the surgical team (physicians, nursing staff, pharmacy, etc.) will be notified about the patients involvement in the trial to ensure standard of care celecoxib and other prohibited therapies are not inadvertently administered.

¹⁵ Patients will complete 1 to 7 days of study therapy prior to surgery and continue twice daily dosing until the last radiation session.

¹⁶ Appendix 3: MDASI Head and Neck Cancer, Appendix 4: EORTC QLQ-H&N43, Appendix 5: Pain Satisfaction Questionnaire, and Appendix 7: Visual Analog Scale for Pain to be completed within 1 month of the scheduled time-points.

¹⁷ Appendix 6: Pre-treatment Questionnaire to be completed at the pre-operation visit.

¹⁸ Patients will be required to record all opioids taken for pain management on Appendix 4: Pain Management Diary while at home. Diary does not need to be maintained during admission post-surgery but should be started when study therapy is started and continue until completion of study therapy.

¹⁹ 5 weeks (\pm 7 days) post-operation the study team will contact the patient to review their medication diary, adverse events, and analgesic use record. If not returning to the study site at this time point, patients will be asked to fax or scan and email their Patient Dosing Diary and Pain Management Diary use records for the study team for review to ensure timely review of study drug compliance.

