10.2 Treatment Period

Once a subject has completed screening, has been found to be eligible, and has been registered, treatment procedures may begin. At the pre-operation visit baseline, questionnaires will be completed and study medication will be dispensed. Patients will be instructed not to begin study medication until 6 days prior to the date of surgery to ensure 5 full days of twice-daily dosing. All pre-operation visit procedures must take place within 14 days prior to surgery unless otherwise noted.

Upon completion of 1 to 7 days of study therapy dosing, patients will undergo head and neck surgery as deemed appropriate by the treating investigator. 14 days (\pm 7 days) after surgery patients will return to the clinic and begin arrangements for adjuvant radiation therapy.

Five to thirty days post-operation every effort should be made to contact the patient to assess study drug compliance and adverse events. For patients not returning to the study site during this time frame, this contact may occur by phone or email. During this contact the study team will check the patient's Dosing Diary, Pain Management Diary, and adverse events. The patient will be asked to scan and email or fax their Dosing Diary and Pain Management Diary for assessment of adherence to the study regimen. However, if the patient does not have access to equipment to do this or is unwilling, failure to obtain the diaries will not be considered a deviation.

During adjuvant radiation, patients will return to clinic for evaluation (Mid-Radiation visit) 5 to 30 days after initiating radiation therapy. Patients will be instructed to continue study therapy twice-daily dosing until completion of their last radiation treatment.

See the Schedule of Events and the Assessments Section for treatment period procedures.

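### The primary model adjusts for provider only and leaves out a pre-dose functional score that may be prognostic: a possible loss of precision, not a bias

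*Combined protocol and SAP*

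**What the plan says.** Section 13.4.1 specifies a Gaussian mixed model for days from surgery to radiation: "The model will contain fixed effects for treatment arm and provider and a nested random effect for patient within provider". It adds: "The mean difference between treatment groups, two-sided p-value and 95% confidence interval will be calculated from the model". No baseline covariate is named there or elsewhere in section 13. Sections 4.2 and 6 make treating provider the only stratification factor.

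Section 13.2 sizes the trial on the total SD: "Assuming Group A mean =72, Group B mean = 57.2, and the common SD =16.2", for which "a two sample t-test with 20 patients in each group will provide 80% power with an alpha = 0.05". The only extra precision it counts on is from control of provider variation.

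Table 4 schedules the Functional Oral Intake score and Karnofsky status at Screening and at Pre-Operation. Footnote 2 requires everything at the pre-operation visit to be finished before study therapy begins. Section 2.3 identifies pain management and functional problems as the leading cause of delay and describes slow recovery with "weight loss, poor oral intake, and reduced overall strength, resulting in delays in initiating adjuvant therapy".

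**The concern.** The protocol's own rationale says that function influences the primary outcome, and it measures one aspect of function, swallowing, before dosing. The primary model then uses none of that information. The patient random effect does not supply it: each patient contributes one value of days to radiation, so that term cannot be separated from the residual.

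With 40 evaluable patients, the width of the confidence interval is the main limit on what the trial can show. If the pre-operation score explains a modest share of the variation between patients, including it would narrow the interval without any new visit. Naming it now also closes off a choice of covariates made after baseline tables have been seen.

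**Working it through.** **Inputs**
- Difference 72 − 57.2 = 14.8 days; SD 16.2; 20 per arm; alpha 0.05 (section 13.2).
- Two-sided test (section 13.4.1; the sample-size text does not state sidedness).
- Number of providers: not in the documents. Four are assumed, and 2 to 8 are checked below.
- R-squared of the score for days to radiation, within arm and provider: not in the documents. A range of 0 to 0.30 is assumed.

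**Step 1: the plan's figure.** SE = 16.2 × √(2/20) = 5.12 days. Noncentrality = 14.8/5.12 = 2.89. The exact two-sided t-test on 38 df has power 80.4%, so the stated 80% is reproduced. (The historical control mean of 72.8 would make the difference 15.6 days and the power 84.3%. The 14.8 used for sizing is kept here.)

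**Step 2: provider-only model.** Four providers as fixed effects leave 40 − 1 − 4 = 35 df. With the SD held at 16.2, power is 80.2% and the 95% CI half-width is 2.030 × 5.12 = 10.40 days. Holding the SD at 16.2 gives no credit for provider variation removed, as in section 13.2.

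**Step 3: add one covariate.** Two things change besides the residual SD. The df fall to 34. The variance of the arm difference also rises by an expected factor of 1 + 1/33, because the covariate will not be perfectly balanced between arms and its slope has to be estimated. So

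SE = 5.12 × √[(1 − R²) × 34/33].

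| Assumed R² | SE, days | Power at 14.8 days | 95% CI half-width, days |
|---|---|---|---|
| provider only | 5.12 | 80.2% | 10.40 |
| 0 | 5.20 | 79.0% | 10.57 |
| 0.05 | 5.07 | 81.0% | 10.30 |
| 0.10 | 4.93 | 83.0% | 10.03 |
| 0.20 | 4.65 | 87.1% | 9.45 |
| 0.30 | 4.35 | 91.1% | 8.84 |

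**Step 4: break-even.** The adjusted interval becomes narrower than the provider-only interval at R² of about 0.03.

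**Step 5: sensitivity to the number of providers.** With 2 to 8 providers, provider-only power runs from 80.3% to 79.9%. Adjusted power runs from 79.2% to 78.5% at R² = 0 and from 87.3% to 86.7% at R² = 0.20. The comparison does not depend on the assumed four.

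**Step 6: why only one covariate.** Under the same variance-inflation approach without provider terms (80.4% unadjusted), two covariates with R² = 0 give 78.1% power and break-even rises to about 0.06. For three and four covariates, break-even is about 0.09 and 0.11.

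**The case against.** The strongest reply is that nothing here is wrong. Randomisation makes the provider-only difference unbiased, its interval and p-value already allow for chance imbalance, the model includes the sole stratification factor, power is about 80% on the stated inputs, and the study is labelled a pilot. All of that stands.

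It is also fair that section 2.3 describes the condition of patients after surgery. That a pre-operative swallowing score predicts the delay is an inference from the rationale, with no figure behind it. This stands too, and it is why the gain is given as a range that includes a loss. Karnofsky status is a weaker choice, because eligibility requires at least 70 and so narrows its range.

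Three stronger readings are tempting, and the documents support none of them.

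- *Early radiation oncology consultation should be a covariate.* Table 4, footnote 13 says: "The radiation oncology consultation should be completed prior to registration if possible". That concerns registration, not surgery. The consultation sits in the Screening column, and a consultation after registration can still precede the operation. Its described content is a discussion of indications, course and side effects, not planning or booking. Section 10.2 has patients come back about 14 days after surgery, when "patients will return to the clinic and begin arrangements for adjuvant radiation therapy". No passage ties the consultation to days to radiation.
- *Adjustment is practically free.* Counting only the lost degree of freedom moves power from 80.20% to 80.14%. That omits the variance factor in Step 3. With it, the cost at R² = 0 is about 1.2 points.
- *Chance imbalance adds error to the arm difference beyond the planned SE.* It does not. The SD of 16.2 is the total SD of historical patients, so variation due to their baseline differences is already inside the SE of 5.12 days.

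**Conclusion.** The point holds as a modest efficiency suggestion. The primary model leaves unused a functional measure that is collected before dosing and belongs to the kind of factor the protocol blames for delay. The effect on power at 14.8 days ranges from a loss of about 1 point (R² = 0) to a gain of about 3 points at R² = 0.10, 7 at 0.20 and 11 at 0.30, with break-even near 0.03.

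This rests on assumed values of R², an assumed four providers, an SD of 16.2 and 20 evaluable patients per arm. A reader might infer that the planned estimate is biased or the test invalid. The documents do not support that: the allocation is randomised, the stratification factor is in the model, and the stated power is reproduced.

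**What to change.** In section 13.4.1, before unblinding, specify a linear model for days from surgery to radiation with arm, provider and the pre-operation Functional Oral Intake score, entered as a linear term and as the only patient-level covariate. Report the adjusted mean difference, its 95% confidence interval and its two-sided p-value as primary. Report the provider-only model as a sensitivity analysis. Because each patient has one value, the patient random effect can be left out of this model.

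The cost is a short change to the analysis text. The score is already scheduled, so no visit or data item is added. The downside is one degree of freedom and about one point of power if the score turns out not to be prognostic.
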